4 STUDY DESIGN

Description of Study Design. This is a randomized single-blind study of uncomplicated *P. falciparum* malaria in adult Malian males (≥ 18 years of age) in which subjects who provide their informed consent to participate will be randomized to either the study arm (1596 mg oral dose of AQ-13 over 3 days) or the control Coartem arm (4 tablets twice daily $\times 3$ days). The rationale for the Coartem controls is to relate the AQ-13 results to Coartem – which is the recommended first-line treatment (current state-of-the-art) for the treatment of uncomplicated *P. falciparum* malaria in sub-Saharan Africa [19-22]. **This is a single-blind study because the subjects will potentially know whether they are receiving AQ-13 (capsules) or Coartem (tablets).** However, the **investigators** evaluating AEs, the relatedness of AEs to the study drugs and other data will not know which subjects were randomized to which arm of the study.

Patient population (Flow Chart 2, page 16, below). The patient population and flow of potential subjects from screening to study accrual are summarized in Flow Chart 2. Recruitment of adult Malian subjects with uncomplicated *P. falciparum* malaria will be performed at the Missira Community Health Center for persons from Missira and the adjacent village of Sirakoroba (total population 6,000) and at the outpatient referral centers in Bamako. Please note that the inpatient studies for all subjects will be performed at the Clinical Research Center and that the subsequent outpatient follow-up visits (twice weekly for 5 weeks) will be at both the Community Health Center in Missira (for subjects from Missira or Sirakoroba) and the Clinical Research Center (for subjects from urban and per-urban regions of Bamako).

Times to obtain Blood Specimens and other Samples and Studies (Flow Charts 3-4, Gantt Chart, pages 17, 26 and 27, below). After providing their informed consent to participate, subjects will be asked to provide 2 tubes of blood for chemistry and hematology testing. Beginning at the time of dosing, participants will also be asked to provide serial blood samples for AQ-13 drug and metabolite blood levels 8, 7 and 7 times on days 1-3, once on days 4 and 5, twice in week 2 (at each of the twice-weekly outpatient visits) and once per week in weeks 3-6 (days 15-42). This information is provided in tabular form and graphically in a Gantt Chart below in Section 7 (page 27). To facilitate the drawing of multiple blood specimens, a heparin lock plastic catheter with a scalp vein needle will be placed in the arm of participants for use during inpatient days 1-4 or 1-5.

Methods for Collecting Blood Specimens. Blood specimens will be obtained by finger stick or through the heparin lock plastic catheter for the screening blood smear, filter paper blot, and Hb, AQ-13 and AQ-13 metabolite levels. Subsequently, they will be obtained by venipuncture for the AQ-13 drug and metabolite levels and for the repeat chemistry and hematology panels beginning on day 4 of the inpatient stay or at the start of outpatient studies in Week 2. A heparin lock (scalp vein attached to a plastic catheter containing heparin to keep the line open) will be placed on inpatient day 1 to permit drawing 24-26 blood samples on inpatient days 1-4 or 1-5 without separate venipunctures for each sample.

Collection of Urine Specimens. To monitor the urinary excretion of AQ-13 and its two major metabolites, subjects will be asked to save their 24 hour urines during inpatient days 1-4.

Expected Duration of Subject Participation from the time of screening and enrollment to the conclusion of their participation in the study is 42 days (6 weeks).

Description of Subject Participation. As noted above, these subjects will be asked to provide or have:

- 32 Tubes of blood for a total volume of 160 ml (5 ml per tube),
- 4 (24 hour) urine collections on inpatient days 1-4,
- 7 Holter recordings at the times of screening (1 hour), during inpatient days 1-4 (24 hours each) and at the 1 and 2 week outpatient follow-up visit (2 hours),
- 2 Eye examinations at the times of screening and the 1 week outpatient follow-up visit.

[figure not shown]
Safety Oversight will be assisted by a Data Safety and Monitoring Board (see section 8.7 on page 33, below).

Flow Chart 2

PROOF OF CONCEPT STUDY FOR AQ-13 ADULT MALES WITH UNCOMPLICATED *P. falciparum* MALARIA

Recruitment in the Villages of Missira and Sirakoroba in Northwestern Mali
and from Outpatient Referral Clinics in the city of Bamako;

In-Patient Studies at the Clinical Research Center, Hôpital Point G in Bamako

Flow Chart 3**PROOF OF CONCEPT STUDY FOR AQ-13
RANDOMIZATION, DRUG ADMINISTRATION AND FOLLOW-UP**

Recruitment in the Villages of Missira and Sirakoroba in Northwestern Mali

and from Outpatient Referral Clinics in the city of Bamako;

In-Patient Studies at the Clinical Research Center, Hôpital Point G in Bamako

EYE EXAMS, HOLTER RECORDINGS, CHEMISTRY PANEL, HEMATOLOGY (CBC)
(n=70; 35 each for the AQ-13 and Coartem groups, expected 5% ineligible).

•INCLUSION CRITERIA:

≥ 2,000 asexual *P. falciparum* parasites per μ l,
Uncomplicated *P. falciparum* malaria,

•Baseline Screening Holter Recording x 1 hour,**•Visual Screening** baseline acuity, visual fields,**•EXCLUSIONS:** Hb ≤ 7 gms/dL, K+ ≤ 3.5 mEq/L, arrhythmias, heart block, BP ≥ 140/90 or severe or complicated malaria.

RANDOMIZE ELIGIBLE ADULT VOLUNTEERS WITH UNCOMPLICATED *P. falciparum* MALARIA
(n=66; 33 each for the AQ-13 and Coartem groups, expected 20% loss to follow-up).

•Filter Paper Blots for molecular studies,**•Freeze Initial Parasites** at -70° C,**•pfcr PCR and other Tests** for CQ Resistance,**•Oral Administration of 700 mg AQ-13 on days 1-2,** followed by 350 mg on day 3, OR

Oral Administration of Coartem, 80 mg artemether

+ 480 mg lumefantrine twice daily x 3 days,

•Repeat Daily Blood Smears (days 1 through 7), repeat Hematology, Chemistry panels on day 4,**•AQ Drug and Metabolite Levels** at 0, 0.5, 1, 2, 4, 6, 12, 18, 24, 24.5, 25, 26, 28, 30, 36, 48, 48.5, 49, 50, 52, 54, 60, 72, 96 and 120 hours x 5 ml,**•Holter Monitoring** 24 hours/day x 4 inpatient days,**•One Week** eye exam, 1 hour Holter recording,**•WITHDRAWAL:** severe or complicated malaria.

FOLLOW-UP
for a total of 6 weeks,
PRIMARY ENDPOINT is
a lack of recrudescence
with the same genotype(s)
(n=28 evaluable subjects/group)

•AQ Drug and Metabolite Blood Levels twice weekly x 1 week, then once weekly in weeks 3-6,**•Filter Paper Blots and Smears** twice weekly x 5 weeks on outpatient follow-up,**•Freeze Parasites for Molecular Studies and Test for Resistance** if parasitemia recurs,**•Repeat 1 hour Holter recording** at the 2 week follow-up outpatient visit.

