QT	Interval from the beginning of ventricular depolarization (start of QRS) to the conclusion of repolarization (end of T wave)
QTc	QT interval adjusted (corrected) for heart rate
SAE	Serious Adverse Event
SOP	Standard Operating Procedure
t $\frac{1}{2}$	Half-Time (for concentration to decrease by 50%)
V_d	Volume of distribution (Liters)
WBC	White Blood Cell
WHO	World Health Organization
X	the percentage of the efficacy of the active control vs. placebo (C – P) that one desires to retain in the investigational drug (I) (see the Statistical Section on pages 37-40)

Title:	AQ-13 for Uncomplicated P. falciparum Malaria: Proof of Concept Study
Population:	Adult Malian males with uncomplicated Plasmodium falciparum Malaria This study will include adult Malian males ≥ 18 years of age in good general health (who have no known medical conditions other than malaria). Subjects who agree to participate and provide their informed consent will be randomized to one of two study arms (33 per arm \times 2 arms = 66 subjects) to receive either AQ-13 (1596 mg orally over 3 days) or Coartem (4 tabs twice daily \times 3 days).
Number of Sites:	There are several initial screening sites at: 1] the Missira/Sirakoroba Community Health Center in the Kolokani District and 2] referral outpatient clinics in and near Bamako. Although there is only one inpatient study site at the Clinical Research Center in Bamako, there will be two study follow-up sites for the 5 weeks of outpatient follow-up: the Community Health Center for Missira and Sirakoroba and the Clinical Research Center in Bamako.
Study Duration:	The duration of this study will be up to 15 months (including follow-up), beginning on June 15 th , 2013 and concluding on or before January 15, 2016.
Subject Duration:	The duration of each subject's participation will be 6 weeks, based on a 1 week inpatient stay for treatment/observation, plus 5 weeks of twice-weekly follow-up.

Primary Objective and Primary Endpoints:

1] The primary objective is to determine and compare the cure rates for AQ-13 and Coartem. Cure is a lack of recrudescence within 42 days (PCR-corrected) – no evidence of recrudescence with the same parasite genotype(s) after reduction of the asexual parasitemia to less than 25% of the admission value by day 3 and clearance of asexual parasites and fever by day 7. Failure is defined as lack of cure.

Secondary Objectives and associated Endpoints for comparisons of AQ-13 with Coartem:

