Indicate the source/site from which the study population will be drawn. The study population of Malian adult males with uncomplicated malaria will be drawn from several outpatient sites: 1] the Missira Community Health Center which serves the adjacent communities of Missira and Sirakoroba 160-170 km northwest of Bamako that have an estimated population of 6,000, and 2] referral clinics in urban and peri-urban Bamako, where >100 outpatients from the urban and peri-urban areas in and around Bamako seek treatment for uncomplicated malaria every day between August and November.

Identify strategies for subject recruitment and retention. Subjects will be recruited from persons who come to the Missira Community Health Center or to clinics that refer to the University of Bamako for the diagnosis and treatment of presumed uncomplicated *P. falciparum* malaria (fever, chills, headache, without signs or symptoms of severe or complicated malaria) [23]. We expect that close personal care and attention during the inpatient week of the study will minimize attrition during that time. To maximize cohort retention for the twice-weekly outpatient follow-up visits during the subsequent 5 weeks, we will provide financial compensation (CFA 5,000=\$10 US) for each outpatient visit and transportation home at the conclusion of each follow-up outpatient visit.

Ability to accomplish participant enrollment and Follow-Up

As noted above and in Flow Charts 2-3, this study is based on the analysis of approximately 28 evaluable subjects in each of the 2 study arms (28 x 2 = 56), and therefore on ≥ 56 evaluable subjects completing the study protocol. To achieve that goal, we expect to screen and enroll substantially greater numbers of subjects. Based on the number of subjects seeking diagnosis and treatment for uncomplicated malaria at the two recruitment sites (≥ 200 per month) and on the inpatient capacity of the Clinical Research Center at the Hôpital Point G (8-10 inpatients), it should be possible to accomplish this study and determine whether the 1596 mg dose of AQ-13 is as effective as Coartem for treatment of uncomplicated malaria.

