7 ASSESSMENT OF OUTCOME MEASURES

7.1 Specification of the Appropriate Outcome Measures

The major question being asked in these studies is whether AQ-13 is efficacious for the treatment of uncomplicated malaria due to *P. falciparum*. Therefore, the major outcome is whether treatment with AQ-13 clears *P. falciparum* parasites from the bloodstream and fever within 7 days without recrudescence within 42 days (3 times the 14-15 day terminal $t\frac{1}{2}$ of AQ-13 in human subjects) [11]. Because the transmission of malaria is often intense in Mali (100-300 bites per person per night during the rainy season), the data for recrudescence will be PCR-corrected [16-17]. Based on the amplification of selected polymorphic loci, recrudescences with parasites different from those in the initial infection will be categorized as new infections, which do not represent treatment failure. Conversely, recrudescences with parasites indistinguishable from those in the initial infection will be categorized as recurrent infections and do potentially represent treatment failures.

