Times to recrudescence and reinfection will be analyzed using life tables, and compared using the log rank test. Cox regression will be used to compare multiple (multivariate) predictors of times to recrudescence and reinfection. Pharmacokinetic parameters will be examined for AQ-13 doses and compared to data from the Phase 1 studies, as appropriate. **Using the same protocol as in the Phase 1 study [11], the relatedness of adverse events (AEs) to study drugs will be classified independently by two blinded physicians according to the definitions in section 8.3 on page 30 as unknown, not related, unlikely to be related, or possibly, probably or definitely related to the study drugs, based on temporal relationships and biological plausibility.** The frequencies of AEs will be compared between AQ-13 and Coartem using Pearson Chi-square. Because more than one AE may occur in an individual patient, the proportion of patients receiving AQ-13 with AEs will be compared with Coartem using Chi-square or the Fisher Exact test. The severity of AEs will be classified using the recent FDA Guidance for Healthy Adult and Adolescent Volunteers in Preventive Vaccine Trials [23], and the severity of AEs across the study arms will be compared using Chi-square. QT interval corrections for heart rate (QTc) will be made using both Bazett's and Fridericia's formulas [41-42]. Within-patient maximum changes from baseline will be assessed using the Wilcoxon test for paired observations. Between-group QT interval changes will be compared using ANOVA or Kruskal-Wallis.

HYPOTHESES BEING TESTED.

The primary hypothesis is that the efficacy of AQ-13 for uncomplicated *P. falciparum* malaria is similar to

that of Coartem - based on a non-inferiority margin of 15%. That is, that AQ-13 will produce a cure rate within 15% of the Coartem control (standard). The secondary hypothesis is that AQ-13 will have safety profiles in subjects with uncomplicated malaria comparable to those for AQ-13 in healthy volunteers [11].

EXPECTED OUTCOMES.

Our preliminary (previous) studies have shown that AQ-13 is:

- *active in vitro* against CQ-resistant and multi-resistant *P. falciparum* [8-9],
- *active in vivo* against CQ-resistant *P. falciparum* in the squirrel monkey model of human infection with CQ-resistant *P. falciparum* (enclosed Figures 1 and 2 in the Appendix), and
- *safe in human subjects* based on Phase 1 studies recently performed in New Orleans [11].

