10.4 RANDOMIZATION

Randomization of individual subjects will be performed after screening is complete, signed informed consent has been obtained, and the inclusion and exclusion criteria have been satisfied and reviewed. Randomization to the 2 treatments (study arms) will involve permuting blocks of 4 and 6 with a random number generator [11]. Only the pharmacist will have access to the computer generated form.

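### Time to recrudescence or reinfection is compared by an unstratified log-rank test, although men are followed in two settings whose reinfection exposure may differ; stratify by follow-up site.

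*Combined protocol and SAP*

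**What the plan says.** The synopsis states that "there will be two study follow-up sites for the 5 weeks of outpatient follow-up". Section 4 assigns them by residence: the "subsequent outpatient follow-up visits (twice weekly for 5 weeks) will be at both the Community Health Center in Missira", for men from Missira or Sirakoroba, and "the Clinical Research Center (for subjects from urban and per-urban regions of Bamako". Section 5.1 places the villages "160-170 km northwest of Bamako that have an estimated population of 6,000".

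The only transmission figure is in Section 7.1. It concerns Mali in general, where transmission is said to be often intense: "100-300 bites per person per night during the rainy season". No biting, incidence or reinfection rate is given for either site.

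Time to recrudescence or reinfection is a secondary outcome (Section 7.1.2). Section 10.3 says: "Times to recrudescence and reinfection will be analyzed using life tables, and compared using the log rank test". The next sentence adds Cox regression on several predictors without listing them. Table 7 gives Kaplan-Meier and Cox as the between-group methods for this endpoint, again without strata or covariates.

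On allocation, Section 10.4 says: "Randomization to the 2 treatments (study arms) will involve permuting blocks of 4 and 6 with a random number generator". It names no stratification factor.

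**The concern.** Men spend the five weeks in which they can be reinfected either in a rural area or in and around the capital. If the risk of a new infection differs between the two, site is a prognostic factor for this endpoint, and it is known before randomisation.

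New infections may well dominate the endpoint. At the planned 95% cure rate, and assuming the same rate for AQ-13, only 0.05 × 66 = 3.3 men are expected to fail. How many would be reinfected is not stated.

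Leaving a prognostic factor out of a log-rank test has two consequences. Pooling high-hazard and low-hazard men pulls the estimated arm difference toward zero, which costs power. And if one arm happens to hold more village men, the pooled test attributes the resulting excess of reinfections to the drug. The Cox sentence does not settle this, because the choice of predictors stays open until the data have been seen.

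**Working it through.** **No plan figure to reproduce.** The 33 men per arm in Section 10.2 were set for the cure-rate comparison. The documents state no power, event count or hazard ratio for reinfection.

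**Inputs from the documents.** 66 men allocated 1:1 in blocks of 4 and 6; two follow-up visits a week in weeks 2-6, to day 42; 20% attrition.

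**Assumed inputs, not in the documents.** Control-arm reinfection risk *p* over 35 days at each site; hazard ratio (HR) for AQ-13; share of rural men (30% or 50%); exponential reinfection times from day 7; dropout uniform over days 7-42; two-sided 5% test.

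**Step 1: dilution from pooling.** The daily hazard is λ = -ln(1 - *p*)/35, multiplied by HR in the AQ-13 arm, so the AQ-13 risk is 1 - (1 - *p*)^HR. Take HR 0.4, half the men rural and 60%/10% (village/Bamako):
- Control arm: mean risk (0.60 + 0.10)/2 = 0.350.
- AQ-13 arm: 1 - 0.4^0.4 = 0.307 and 1 - 0.9^0.4 = 0.041; mean 0.174.
- Ratio of pooled cumulative hazards: ln(1 - 0.174)/ln(1 - 0.350) = 0.191/0.431 = 0.44, against 0.40 within each site.

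The same arithmetic gives 0.42 at 40%/10% and 0.50 at 80%/10%.

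**Step 2: power.** The log-rank statistic is Z = Σ(O - E)/√ΣV. The stratified version forms O, E and V within each site and then sums them. Each entry rests on 3,000 simulated trials (4,000 for 80%/10% with half rural), with simulation error of about 1 point. Power is shown unstratified → stratified at HR 0.4.

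| Village/Bamako risk | Half rural | 30% rural |
|---|---|---|
| 30%/30% | 35% → 34% | 35% → 34% |
| 40%/10% | 29% → 31% | 22% → 23% |
| 60%/10% | 33% → 40% | 25% → 29% |
| 80%/10% | 37% → 54% | gain about 12 points |
| 80%/5% | 34% → 53% | 20% → 35% |

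At HR 0.4 and a milder contrast with half rural, the changes are 32% → 33% (40%/20%) and 44% → 47% (60%/20%). At HR 0.6 the gain is about 1 to 8 points when the sites differ clearly and none at 40%/20% (14% either way). At HR 0.8 power is 6-8% with either test.

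**Step 3: type I error with no drug effect, half rural.** Unstratified 4.4% (60%/10%) and 4.3% (80%/5%); stratified 5.0% and 5.7%.

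**Step 4: chance imbalance.** With K rural men among 66 and 33 per arm, the number x in one arm is hypergeometric (treating site as unrelated to block order), and the arms' rural shares differ by |2x - K|/33.
- K = 33: a gap of at least 20 points needs x ≤ 13 or x ≥ 20; probability 13.9%.
- K = 20: it needs x ≤ 6 or x ≥ 14; probability 5.9%.

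With the number of rural men left to vary, the simulated frequency is about 7-12%. At 60%/10%, a 20-point gap alone produces 0.20 × 50 = 10 points of difference in reinfection. Within those imbalanced trials, with no drug effect and unequal sites, the unstratified test is falsely positive in about 8-27%. The stratified test stays near 5%.

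**Step 5: does the randomisation need to change?** With separate lists per site (half rural, HR 0.4), the stratified test has 41% power at 60%/10% and 52% at 80%/5%, against 40% and 53% with one list. The unstratified test stays at 32% and 28%. The gain comes from the analysis, not from the allocation.

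**The case against.** The case against making much of this is substantial.

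- **The site contrast is not documented.** A reader might infer from village versus city that the two places are known to have very different transmission. The documents do not say so. Section 5.1 reports more than 100 outpatients a day seeking malaria treatment in and around Bamako from August to November, so Bamako is not shown to be low-risk. This stands: the size of the gain is conditional, and large gains need both a steep contrast and a strong drug effect.
- **Cox is planned.** Table 7 lists it as a between-group method, so the plan does not rule out a site term. This stands too. What is missing is the commitment to use one.
- **Type I error is sound.** A reader might infer that chance imbalance makes the planned test invalid. It does not: over all randomisations the error rate is about 5%. The protection in Step 4 applies to the particular trial in which an imbalance occurs.
- **The randomisation is not defective.** Unstratified blocks are acceptable in a 66-man trial dosed at one inpatient centre.
- **The endpoint is secondary.** A reader might extend the point to the primary result. New infections are not failures in the PCR-corrected cure rate. Section 6.7 ends participation at any recurrence, so reinfection could shorten observation for recrudescence, but no effect on the cure comparison has been shown. No power target or decision rule is attached to time to reinfection, and stratified power stays between 23% and 54% in the unequal-site scenarios of Step 2 at HR 0.4.

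None of this argues against naming the stratum, because the cost is so small.

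**Conclusion.** The point holds as a modest improvement to a secondary analysis. Follow-up site is fixed by residence and may be prognostic for reinfection, yet neither the log-rank test nor the Cox model names it.

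At HR 0.4, with 30-50% rural and 20% attrition, stratifying changes power by about -1 to 0 points if the sites are equal, 0 to +3 at 40%/10%, +4 to +7 at 60%/10% and +12 to +17 at 80%/10%. Gains shrink with weaker drug effects. Every site risk, the hazard ratio and the rural share are assumptions. The trade is uneven: about 1 point at worst, against a useful gain and protection from chance imbalance if the sites do differ.

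**What to change.** In Section 10.3 and Table 7, state that the log-rank test and the Cox model for time to reinfection, and for time to any recurrence, are stratified by follow-up site (Missira/Sirakoroba versus Bamako). Define site by the residence-based assignment at enrolment, and fix the wording before unblinding so that the choice cannot appear data-driven.

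The cost is one phrase in the analysis plan. It needs no extra men, visits or measurements, and the expected loss is about 1 point of power if the sites prove equal. If randomisation has not begun, the pharmacist could hold one block list per site; this is optional and not needed for the gain.
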